Remind subject to obtain 7-point glucose data for	X				X			X			X			X					

Phase	Screening	PK	Titration period														End of Titration	Follow-up	Early Termination ^a
			3	4	5	6	7	8	9	10	11	12	13	14	15	16			
Visit number	1	2	3	4	5	6	7	8	9	10	11	12	13	14	15	16			
Day	D-21 to D-7	D1	D2	D4	D6	D8	D10	D12	D15	D17	D19	D22	D24	D26	D29	D36			
Visit window (days)			0	± 1	± 1	± 1	± 1	± 1	± 1	± 1	± 1	± 1	± 1	± 1	± 1	± 3			
next site visit ^g																			
Blood glucose via glucose meter reading		X ^h	X	X	X	X	X	X	X	X	X	X	X	X	X	X			
Review subject's 7-point glucose data						X			X			X			X				
AFREZZA® and basal insulin																			
BluHale inspiratory training		X																	
Training on use and storage of AFREZZA® inhaler and cartridge		X																	
Dispense new AfreZZA inhalers and cartridges as necessary ⁱ		X				X			X			X			X		X		
Breakfast and lunch at site		X																	
AFREZZA® inhalation		X																	
Dose titration			X	X	X	X	X	X	X	X	X	X	X	X	X				

Phase	Screening	PK	Titration period														Follow-up	Early Termination ^a
			3	4	5	6	7	8	9	10	11	12	13	14	15			
Visit number	1	2														16		
Day	D-21 to D-7	D1	D2	D4	D6	D8	D10	D12	D15	D17	D19	D22	D24	D26	D29	D36		
Visit window (days)			0	± 1	± 1	± 1	± 1	± 1	± 1	± 1	± 1	± 1	± 1	± 1	± 1	± 3		
based on SMBG values																		
Provide nutritional information		X																
Prescription for usual prandial RAA															X		X	
Pharmacokinetics																		
Insulin PK sampling for 4 hours		X																
FDKP PK sampling for 4 hours		X																
Anti-insulin antibody	X														X		X	

Abbreviations: β-HCG, beta human chorionic gonadotropin; BG, blood glucose; ECG, electrocardiogram; FDKP, fumaryl diketopiperazine; HbA1c, glycated hemoglobin

A1c; PK, pharmacokinetic(s); RAA, rapid-acting analog; SMBG, self-monitored blood glucose.

- Early termination is defined as withdrawal or discontinuation at any point between AFREZZA® administration on Day 1 (Visit 2) and end of 28-day titration.
- Tests for hepatitis B antigen, hepatitis C antibodies, anti-HIV-1, and anti-HIV- 2.
- Urine β-HCG test to be done in female subjects of childbearing potential in Cohorts 1 and 2.
- Spirometry: on Day 1 Spirometry test will be conducted at approximately –25, 18, 55, 125, and 245 minutes.

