- Blood glucose sample for 4 hours: glucose reading to be done locally via a table top glucose meter (eg, YSI) at Investigator site. Central laboratory will be used only if local reading (i.e., table top glucose meter) is not available.
- Additional test strips may be provided as needed at Visits 6, 9, 12, 15 and every 3 months during the extension treatment period.

- g. Once per week in the week prior to the next clinic visit, subjects will obtain 7-point glucose data (pre-meal and 120-150 minutes post-dose at breakfast, lunch, dinner, and pre-bedtime). On these days, the starting and ending time for each meal will be recorded in the e-Diary, in addition to the dosing time.
- h. If the fasting plasma glucose (FPG) value is ≥ 80 mg/dL at Visit 2, the subject will undergo a 4-hour PK assessment after eating his/her usual breakfast and receiving his/her breakfast dose of AFREZZA®.
- i. One inhaler, which may be used for up to 15 days, and replacements will be available if necessary.

1.2 SCHEDULE FOR DAY 1

Day	D1																											
Time (minute)	-30	-25	-15	0	5	10	15	18	20	30	45	55	60	90	120	125	180	240	245	250								
Indicative clock time	7:30 am	7:35 am	7:45 am	8:00 am	8:05 am	8:10 am	8:15 am	8:18 am	8:20 am	8:30 am	8:45 am	8:55 am	9:00 am	9:30 am	10:00 am	10:05 am	11:00 am	12:00 pm	12:05 pm	12:10 pm								
Concomitant medications	<	-	-	-	-	-	-	-	-	-	-	-	-	-	-	-	-	-	-	>								
Adverse event collection	<	-	-	-	-	-	-	-	-	-	-	-	-	-	-	-	-	-	-	>								
Blood glucose via glucose meter reading ^a	X																											X
Glucose value via local or central laboratory ^b				G00							G01				G02	G03	G04		G05	G06								
Spirometry (FEV ₁)		X						X				X						X			X							
Study treatment administration																												
AFREZZA® inhalation				X ^c																								X ^e
Meal				X ^d																								X ^e
Pharmacokinetics																												
Human insulin	S00		S01	S02	S03	S04	S05		S06	S07	S08		S09	S10	S11		S12	S13										
FDKP				SF00			SF01			SF02				SF03			SF04											

Abbreviations: FEV₁, forced expiratory volume in 1 second; FDKP, fumaryl diketopiperazine;

- If the FPG value is ≥ 80 mg/dL at Visit 2, the subject will undergo a 4-hour PK assessment after eating his/her usual breakfast and receiving his/her breakfast dose of AFREZZA®.

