12 STUDY PROCEDURES

12.1 VISIT SCHEDULE

MKC-TI-155 Part 1 consists of:

- A 7 to 21-day screening period
- A 1-day in-clinic PK assessment
- A 28-day outpatient study of the safety and ability to titrate AFREZZA in children ages 4 to 17 years with T1DM

All visits to the clinical sites should take place in the morning at approximately the same time. For telephone-call visits, the subject is called by the Investigator or qualified designee at a pre-scheduled time.

A timeframe of ± 1 days using the day of Visit 2 as reference is acceptable. The post-treatment follow-up Visit 16 should occur 1 week ± 3 days after the last treatment.

If a visit date is changed, the next visit should take place according to the original schedule.

If a subject withdraws consent to participate in the study, or his/her physician decides participation is no longer in the subject's best interest, an end of treatment visit should be conducted to evaluate the subject's health status as soon as possible if the subject is willing and in the physician's opinion able to do so.

For a complete list of procedures scheduled for each study visit, please refer to the Study Flow Charts (1.1 and 1.2). The following sections provide additional details about how some of the procedures will be performed.

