12.1.3.3 Telephone contact (Visits 7, 8, 10, 11, 13, and 14)

There will be a safety/dose titration telephone contact after site Visits 6, 9, and 12. Adverse events and concomitant medications will be reviewed, and the subjects' prandial doses will be adjusted for each meal according to [Table 2](#) and their basal doses according to [Section 8.1.7](#). Subjects will also be instructed to obtain 7-point glucose data (pre-meal and 120-150 minutes post-dose at breakfast, lunch, and dinner as well as pre-bedtime during one 24-hour day) prior to the next visit.

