8 STATISTICAL METHODS

8.1 General Considerations

In this study, unless otherwise specified, all analyses will be performed in a descriptive manner by age cohort (including ‘Cohort 1’, ‘Cohort 2’, ‘Cohort 3’ and ‘Total’). The ‘Total’ group will include all subjects in the analysis population.

Where appropriate, all dimensions will be summarized in metric units, but listings will, in addition, represent values as collected.

For continuous variables, the number of subjects, mean, standard deviation, median, minimum, and maximum values will be displayed, as appropriate according to the type of data. The minimum and maximum will be displayed to the same number of decimal places that the data were recorded to. The mean and median will have 1 extra decimal place and the standard deviation will have 2 extra decimal places. The geometric mean and coefficient of variation (CV) will have 2 extra decimal places. Confidence interval (of the mean) will have the same decimal precisions as the mean.

For categorical variables, frequency counts and percentages of total for each category will be presented; missing values will be treated as a separate category, where appropriate. Percentage will be presented in 1 decimal place.

Visit specific data (e.g., 7-point SMBG or pulmonary function tests) will be summarized by analysis visit, which is defined based on the visit windows specified in Section 0

Non-visit specific data (e.g., hypoglycemic events or daily dose) will be summarized by study period and/or by time interval. See relevant sections for more details.

8.1.1 **Data Handling/Imputation Methods**

8.1.1.1 **Missing Data Imputation**

Unless otherwise specified, missing data other than start date of adverse events (AE) or start/end date of concomitant medications (CM) will not be imputed.

The imputation rules for start date of Aes and start/end date of CMs are as follows:

Adverse Events

- Start date
 - If the start date is completely missing, the start date is set to the date of first dose.
 - If the year is present and the month and day are missing or the year and day are present and the month is missing:

If year = year of first dose, then set month and day to month and day of first dose

Version Date: 17-Jan-2020

- If year < year of first dose, then set month and day to December 31.
- If year > year of first dose, then set month and day to January 1st.
- If the month and year are present and the day is missing:
 - If year = year of first dose and

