8.1.1.2 Visit Window

Visit windows are defined for visit-specific parameters as following:

Table 2 Visit Window

Parameter	Study Period	Analysis Visit	Target Relative Day (s)*	Visit Window (Relative Days)*
HbA1c, Anti-insulin antibody	Screening	Screening	-21 to -7	[Day of ICF signed, - 1]
	Titration	Week 4 (Visit 15, EOT)	29	[22, 36]
	Extension	Month 12 (Visit 28, EOT)	Start day of the extension period + 365	[Start day of the extension period + 337, End day of the extension period + 393]
FEV ₁	Screening	Screening	-21 to -7	[Day of ICF signed, - 1]
	Titration	Day 1	1	No visit window, data collected on that day will be summarized by nominal time point
		Week 2 (Visit 9)	15	[8, 21]
		Week 4 (Visit 15, EOT)	29	[22, Treatment end day of the titration period]
		Follow-up	36	[Treatment end day of the titration period + 1, End day of the titration period]. Only subjects who opt not to participate in the extension period should have this visit.
	Extension	Month 3	Start day of the extension period + 91	[Start day of the extension period + 77, Start day of the extension period + 105]
		Month 6	Start day of the extension period + 183	[Start day of the extension period +169 , Start day of the extension period +197]
		Month 9	Start day of the extension	[Start day of the extension period +260, Start day of the extension period +288]

Parameter	Study Period	Analysis Visit	Target Relative Day (s)*	Visit Window (Relative Days)*
			period + 274	
		Month 12 (Visit 28, EOT)	Start day of the extension period + 365	[Start day of the extension period + 351 , Treatment end day of the extension period]
		Follow-up	Start day of the extension period + 396	[Treatment end day of the extension period +15, End day of the extension period]
Vital Signs and 7-Point SMBG	Screening	Screening	-21 to -7	[Day of ICF signed, - 1]
	Titration	Day 1	1 (for Vital Signs only)	No visit window, data collected on that day will be summarized by nominal time point
		Week 1 (Visit 5)	8	[5, 11]
		Week 2 (Visit 9)	15	[12, 18]
		Week 3 (visit 12)	22	[19, 25]
		Week 4 (Visit 15, EOT)	29	[26, Treatment end day of the titration period]
		Follow-up (for Vital Signs only)	36	[Treatment end day of the titration period +4, End day of the titration period]. Only subjects who opt not to participate in the extension period should have this visit.
	Extension	Month 3	Start day of the extension period + 91	[Start day of the extension period + 77, Start day of the extension period + 105]

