		Month 6	Start day of the extension period + 183	[Start day of the extension period +169 , Start day of the extension period + 197]
		Month 9	Start day of the extension period + 274	[Start day of the extension period +260 , Start day of the extension period +288]

Parameter	Study Period	Analysis Visit	Target Relative Day (s)*	Visit Window (Relative Days)*
		Month 12 (Visit 28, EOT)	Start day of the extension period + 365	[Start day of the extension period +351 , Treatment end day of the extension period]
		Follow-up (for Vital Signs only)	Start day of the extension period + 396	[Treatment end day of the extension period + 15, End day of the extension period]

* Start/end day is calculated as the corresponding start/end date – Study Day 1 +1.

- Data will be assigned to analysis visits using the date of measurement and the visit windows (see [Table 2](#) above).
- If multiple measurements are collected within the same visit window, (1) for Screening visit, the last measurement will be used for analyses; (2) for post-baseline visits, the measurement that is closest to the target relative day will be used for analyses. In the event of a tie, the later measurement will be selected for analyses.
- In addition to the analysis visits listed in the table above, a visit of ‘Early Termination’ will also be included, for both the titration period and the extension period. For subjects with early discontinuation, data collected at the Early Termination visit will be summarized and presented at that visit, no matter whether the data has fallen into the visit window of any other visit or not (i.e., for example, if the value from Early Termination visit also falls into the visit window of Week 4, it will be summarized both with the Week 4 data, and with the other data collected at the Early Termination visit). By doing so, special attention can be drawn to the data collected at Early Termination, so if there is any particular safety data pattern associated with early discontinuation, it could be more easily recognized.
- Values which are not collected at Early Termination visits and do not fall into any of the visit windows will not be included in by-visit data summary, but will be presented in subject-listings
- If measurements are taken at multiple scheduled time points on the same day, data will be summarized based on nominal time points. Data collected at unscheduled time points will not be used for analyses.

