8.4.5 Fasting pre-breakfast SMBG and post-prandial SMBG

Schedule and Parameters

Fasting pre-breakfast SMBG and post-prandial SMBG at each meal will be measured daily throughout the study.

Table presentation

For each of the four parameters (fasting pre-breakfast SMBG and post-prandial SMBG at breakfast, lunch and dinner), average will be calculated at weekly intervals for the titration period and at monthly intervals for the extension period for each subject, and summarized by cohort. Same as for total daily dose and prandial dose, only data collected in the 2nd half of each interval (i.e., within 3 days prior to the each clinic visit in the titration period and within 2 weeks prior to each visit in the extension period) will be included in the analysis.

Baseline is defined as the average of all values collected prior to Visit 2. Change from baseline for a post-baseline time interval will be calculated as average of SMBG in the post-baseline time interval – baseline for each subject, and then summarized by cohort.

Graphical Presentation

For each of the four parameters, a Mean (SE) plot will be provided, presenting weekly average in the titration period and monthly average in the extension period (along with standard error) by cohort.

8.4.6 7-point SMBG

Schedule and Parameters

7-point SMBG (pre-meal and 120-150 minutes post-dose at breakfast, lunch and dinner as well as at bedtime) will be collected at screening visit, visits 6, 9, 12, 15 in the titration period, and visits 19, 22, 25, 28 in the extension period.

Table presentation

For each of the 7 parameters (pre-meal and 120-150 minutes post-dose 7-point SMBG at breakfast, lunch and dinner as well as at bedtime), average will be calculated at weekly intervals for the titration period and at monthly intervals for the extension period for each subject, and summarized by cohort. For each of these intervals, all data collected from the date of the previous on-site visit (including) to 1 day before the current visit for each visit are included in the summary.

Baseline is defined as the average of all values collected prior to Visit 2. Change from baseline for a post-baseline time interval will be calculated as average of 7-point SMBG in the post-baseline time interval – baseline for each subject, and then summarized by cohort.

Subject Listings

Detailed information of every measurement will be listed, by (in the order of) cohort, investigator site, subject and visit.

Graphical Presentation

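### The SAP places 7-point SMBG profiles in titration weeks by two conflicting rules, and the Table 2 windows can put protocol-compliant profiles in the previous week

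*SAP*

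**What the plan says.** **When profiles are taken.** Note g to the protocol flow chart (1.1) reads: "Once per week in the week prior to the next clinic visit, subjects will obtain 7-point glucose data". In titration the clinic visits are Visits 6, 9, 12 and 15, on Days 8, 15, 22 and 29. Protocol 12.1 lets visits move by one day either way ("days using the day of Visit 2 as reference is acceptable").

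**When subjects are prompted.** The flow-chart row that begins "Remind subject to obtain 7-point glucose data for" is marked at screening and at Visits 5, 8, 11 and 14, that is Days 6, 12, 19 and 26. Protocol 12.1.3.1 confirms Visit 5. Protocol 12.1.3.3, which covers the calls at Visits 7, 8, 10, 11, 13 and 14 together, says: "Subjects will also be instructed to obtain 7-point glucose data". As written, that includes Days 10, 17 and 24.

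**First SAP rule.** Section 8.1 states: "Visit specific data (e.g., 7-point SMBG or pulmonary function tests) will be summarized by analysis visit". In Table 2 (8.1.1.2) the row "Vital Signs and 7-Point SMBG" sets Week 1 as [5, 11], Week 2 as [12, 18], Week 3 as [19, 25] and Week 4 as Day 26 to the end of titration treatment. If a window holds several values, the one nearest the target day is kept, and a tie goes to the later one. Values that "do not fall into any of the visit windows will not be included in by-visit data summary" are listed only, apart from Early Termination data.

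**Second SAP rule.** Section 8.4.6 averages, for each subject and interval, "all data collected from the date of the previous on-site visit (including) to 1 day before the current visit for each visit".

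**No rule.** Section 8.4.7 summarises the profile mean by visit, summarises the 7-point data again by visit and time point, and plots mean curves at screening, Visit 15 and Visit 28. It does not say which rule selects the profiles.

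**The concern.** A window of visit day plus or minus three suits a measurement made at the visit, such as vital signs. A 7-point profile is a diary record completed before the visit, so half of that window lies where no profile for that visit is due. The earlier part of the collection week belongs to the previous visit's window.

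The two rules differ in the interval, in the selection (one profile against an average) and in the baseline. Section 8.1.1.2 takes the last screening value, while 8.4.6 averages everything before Visit 2. A programmer working on 8.4.7 would fall back on Table 2, because 8.1 names 7-point SMBG as data it governs.

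At stake is the description of glucose through titration. Week 4 could lose subjects who did their Visit 15 profile on time, and the Week 1 to Week 3 summaries could contain profiles from the following dosing week. With about 14 to 18 subjects per cohort, a few shifted profiles can change the n and the mean at a visit.

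**Working it through.** **Inputs.** Target days 8, 15, 22 and 29, the windows and the nearest-to-target rule come from SAP 8.1.1.2. The collection week comes from protocol note g. Call days come from the flow chart and protocol 12.1.3.3. Assumptions: nominal clinic days, one profile per week, and titration treatment ending on Day 28 or later.

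**Step 1: reproduce the windows.** Target ± 3 gives 8 ± 3 = [5, 11], 15 ± 3 = [12, 18], 22 ± 3 = [19, 25] and 29 − 3 = 26. These match Table 2. Week 4 is not centred, because it runs on to treatment end.

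**Step 2: the 8.4.6 intervals.** With clinic visits on Days 1, 8, 15, 22 and 29, they are Days 1–7, 8–14, 15–21 and 22–28. This is the protocol's collection week, so all 27 days from Day 2 to Day 28 go to the visit they were taken for.

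**Step 3: the same days under Table 2.**

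| Profile for | Compliant days | Right visit | One week early | No window |
|---|---|---|---|---|
| Visit 6 | 2–7 | 5–7 (3) | none | 2–4 (3) |
| Visit 9 | 8–14 | 12–14 (3) | 8–11 (4) | none |
| Visit 12 | 15–21 | 19–21 (3) | 15–18 (4) | none |
| Visit 15 | 22–28 | 26–28 (3) | 22–25 (4) | none |
| Total | 27 | 12 | 12 | 3 |

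**Step 4: dependence on the prompt.** The table counts the days from each prompt to the day before the visit. The last two columns weight those days equally. The final column covers the case where the Visit 12 and Visit 15 profiles both fall in the Week 3 window and the Visit 12 profile is nearer Day 22.

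| Profiles done | Days | Right | Early | No window | Week 4 empty | Visit 15 profile used nowhere |
|---|---|---|---|---|---|---|
| After flow-chart call, nominal day | 11 | 11 | 0 | 0 | 0/3 = 0% | 0% |
| After flow-chart call, one day early | 15 | 12 | 3 (Days 11, 18, 25) | 0 | 1/4 = 25% | 2/16 = 12.5% |
| From the first call covered by 12.1.3.3 (Visit 5 for Visit 6) | 17 | 11 | 6 (Days 10–11, 17–18, 24–25) | 0 | 2/5 = 40% | 3/25 = 12% |
| Any compliant day | 27 | 12 | 12 | 3 | 4/7 = 57% | 3/49 = 6% |

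**Example.** A Visit 12 profile on Day 21 and a Visit 15 profile on Day 24 are both compliant, and both fall in Week 3. Their distances from Day 22 are 1 and 2, so the Visit 15 profile is discarded and Week 4 is empty.

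**Step 5: extension rows.** Windows there open 14 days before the target, so all seven days before each target visit fall in the right window. The problem is confined to titration.

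**The case against.** The strongest reply is that the flow chart and Table 2 fit together. The reminders fall on Days 6, 12, 19 and 26, and the windows open on Days 5, 12, 19 and 26. A site that calls on the nominal day, with a subject who waits for the call, gets the same visit under both rules. This stands, and it makes the effect conditional. It does not remove the conflict, because note g allows any day of the week, calls may come a day early, and 12.1.3.3 places the instruction at earlier calls too.

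Three stronger inferences are not supported.

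- *That 57% of profiles are misplaced.* This needs an even spread of profile days, which nothing in the documents supports. It also fails for Visit 6, where the early days have no previous window to move into. Nor does 12.1.3.3 order a profile on Days 10, 17 or 24. It asks for one before the next visit.
- *That the Visit 15 profile disappears.* When it is displaced it is usually reported as Week 3, and it stays in the listings.
- *That two tables will contradict each other.* Appendix 3 lists one table by time point and visit (14.4.4.1) and one of a different statistic, the profile mean (14.4.4.2). The n in the second can differ anyway, because profiles with more than three missing points are skipped.

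It is also fair that profiles on Days 2 to 4 are unlikely, since the prompt for that week comes at Visit 5. The stakes are modest too. 7-point SMBG sits under Other Endpoints (SAP 8.4), is not a listed PK or safety endpoint, is not marked for the DMC package, and is not the daily postprandial SMBG named in the titration objective, which 8.4.5 analyses by its own rule.

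Finally, 8.4.6 could be read as a specific rule overriding the general one. That would settle its own summaries but not those of 8.4.7.

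**Conclusion.** The conflict is real and should be resolved before the outputs are programmed. Two stated rules give different week labels for compliant profiles, and the one that 8.4.7 would inherit by default is the one that does not match how the protocol collects the data.

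The size depends on behaviour the documents do not fix. It runs from no profiles affected, through 3 of 15 days with calls one day early and 6 of 17 from the first calls covered by 12.1.3.3, to 15 of 27 days if every compliant day is counted. These are counts of permitted days on the nominal schedule and do not forecast how many profiles will be misplaced.

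The baseline conflict has a similar limit. Protocol 9.2.6.3 asks for one screening profile, so the two definitions differ only where a subject records more than one.

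All affected outputs are descriptive. No test, sample size or listed PK or safety endpoint depends on them.

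**What to change.** 1. In SAP Table 2, remove 7-Point SMBG from the titration rows, and amend 8.1 so that it no longer cites 7-point SMBG as window-assigned data in titration.
2. State that the 8.4.6 interval applies to every titration 7-point output, including the 8.4.7 tables and figures and the Visit 15 mean curve.
3. State one baseline rule for all 7-point outputs: either the last screening value or the average of all values before Visit 2.
4. For 8.4.7, say how two profiles in one interval are handled, for example by averaging them as in 8.4.6.
5. Reconcile protocol 12.1.3.3 with the flow chart on which calls carry the profile instruction. The analysis does not depend on the answer once item 2 is adopted. Sites also use these profiles when reviewing dosing, so the choice belongs to the study team.
6. While editing Table 2, correct the Week 1 label: it cites Visit 5, but target Day 8 is Visit 6.

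The cost is SAP wording, a small programming change and one protocol clarification. No new data are needed.
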